**9) Potential benefits to subjects and/or society**

It is not anticipated that subjects will derive direct benefit from participation in the proposed study. However, it is anticipated that findings from this study will help to advance scientific and medical understanding of treatment of mTBI and sleep disorders.

The study will provide basic scientific information about the effects of short wavelength light on sleep patterns and potential rate of recovery from mTBI. Such information may improve the ability to treat sleep disorders and cognitive performance among patients with mTBI.

The diagnostic assessment and heart rate measures may reveal previously unidentified psychiatric and/or cardiac abnormalities subjects didn't know they had. If any abnormalities are identified, they will be provided with information about the finding and encouraged to follow up with their primary care physician. Subjects will be made aware that we are not providing psychiatric, neuroradiological, or other clinical services; only that we will let them know in the event that anything abnormal is noticed by the study team. We are unable to assume responsibility or offer compensation for related medical costs that they make as a result of being informed of an abnormal finding.

There may be instances in which an abnormality exists but is not identified in our analyses. Our team is not trained in clinically diagnosing issues pertaining to abnormalities found in the collected data. Further, our data analyses are not intended to treat, diagnose, or replace the expertise of a medical doctor or a medical diagnosis. Thus, they should not rely on our analyses to reveal abnormalities in your data, and our lab claims no responsibility for abnormalities that go undetected during their participation in any research related activities.

**10) Provisions to protect the privacy of subjects and the confidentiality of data**

Collected data will be computerized. A unique study-specific ID number will be assigned to each subject and used for identification purposes. A separate password-protected data file, stored on a stand-alone PC, will maintain the ID number and identifying information for each participant. Only the PI and Project Coordinator will have access to that file. Personally identifying information (e.g.,

**FORM: Application for Human Research**

NUMBER	FORM DATE	PAGE
F200	02/2014	33 of 39

name, social security number, date of birth) will not be included on any research record that has the subject's ID number.

Communication through the 3rd party marketing campaign (Twilio) will connect interested individuals to study staff via their medadmin email accounts and to dedicated secure study phone lines. The company retains a call log and SMS message history, which is also sent to the SCAN Lab. All call and SMS message history will be wiped from the company's servers every 24 hours and removed from the SCAN Lab's database as soon as study staff respond to any calls or text messages (no later than the next business day). At no point does any subject "subscribe" or "opt-in" to any system. This is voluntary and participants may elect to not receive SMS-based communication.

All information regarding experimental subjects will be kept in a locked file cabinet in the University of Arizona Department of Psychiatry. The signed consent forms will be stored separately from the research data in a locked file cabinet in the Department of Psychiatry. Any study forms that contain personally identifying information for our participants (e.g., signed consent forms, payment information) will be kept separately from research records and data in separate locked filing cabinets in the Department of Psychiatry. All subject voice recordings will be used to verify that the study team collected complete responses and will be verified and deleted the same day they are collected. These recordings will only be linked to subject IDs during that period.

The Imaging Center will be provided with Subject ID numbers only to avoid creating any additional PHI. MR Records will be kept indefinitely in a locked office. Subject identifying codes such as the subject's MRN (medical record number) will not be used for research data. All HIPAA requirements will be followed.

Research data will be stored in a secure area indefinitely.

A Certificate of Confidentiality has been obtained from NHLBI (National Heart, Lung and Blood Institute) for this study.

## **11) Cost to subjects**

Subjects will not incur any costs for participation in this study, save for their time. Their participation is expected to last 7 weeks if they see their participation to conclusion, or up to 13 weeks if they participate in all 6 weeks of follow-up sleep monitoring.

## **12) Subject compensation**

### **Main Study Arm:**

Subjects will receive \$1000 for completion of both study sessions and successful adherence to the daily light exposure treatment. This payment is also intended to cover all transportation expenses to and from the hospital.

If subjects choose to withdraw from the study prematurely, they will be compensated at a rate of \$25/hour for the time they were undergoing scanning and testing, according to the following schedule:

**FORM:** Application for Human Research

NUMBER	FORM DATE	PAGE
F200	02/2014	34 of 39

- Discontinuation during or following the initial visit, subjects will be paid \$50 for completing the initial clinical assessment and questionnaires.
- Discontinuation before the end of second visit (i.e., first testing and scanning session): \$25/hour, up to a maximum of \$250 total, following return of all study-related equipment.
- Discontinuation any time during the 6-week light exposure period: \$275 maximum total payment, following return of all study-related equipment.
- Discontinuation during but before the end of the third visit: \$275 plus \$25/hour during the third visit, up to a maximum total payment of \$475, following return of all study-related equipment.
- Completion of study procedures up to the end of the third visit and return of all study equipment: \$900.
- Completion of all study procedures up to the end of the third visit, return of all study equipment, and evidence that all at-home study procedures were followed (i.e., regular compliance with the use of wrist activity monitors, sleep diaries, and light exposure device): \$1,000. If subjects fail to return the Actiwatch and/or Light Device, subjects will receive no compensation.

If subjects choose to participate in the 6-week follow-up period after the initial 7 weeks:

- Discontinuation at any time during the 6-week period post light therapy: \$1,000 plus \$33.33/week for each week of participation after the end of the third visit.
- Completion of all study procedures for the entire duration of the study (13 weeks), including return of all study equipment within 10 days and evidence that all at-home procedures were followed (i.e., regular compliance with the use of wrist activity monitors and sleep diaries): \$1,200.

**Healthy Control/Effect Localization Arm:**

Subjects will receive \$200 for completion of the assessment, light exposure, brain imaging scans and return of the Actiwatch. This payment is also intended to cover all transportation expenses to and from the hospital.

If subjects choose to withdraw from the study prematurely, they will be compensated at a rate of \$8.05/hour for the time they were undergoing scanning and testing (up to a maximum of \$40.00).

Compensation will mirror current minimum wage. The initial visit is expected to take approximately 5 hours at \$8.05/hour. Subjects will receive a bonus of \$160.00 for returning for the follow-up visit, expected to take approximately 30 minutes, the same day for final saliva collection and returning the Actiwatch. Should the subject not return for the follow-up visit or return for the follow-up, but not return the Actiwatch, they will not receive compensation. In the event the subject returns for the follow-up, but the Actiwatch is broken, the subject will still receive the maximum compensation of \$200.00.

All reasonable steps will be taken to prevent undue influence, and the study team feels that the compensation schedule reflects reasonable compensation for participation given the study activities involved.

**FORM: Application for Human Research**

NUMBER	FORM DATE	PAGE
F200	02/2014	35 of 39

Subjects who are recruited from the PSY101 course will receive up to 4 credits as part of their compensation for participation. Their financial compensation will not be affected.

**13) Medical care and compensation for injury**

Subjects will be offered the care needed to treat any injury that directly results from taking part in this research study. We reserve the right to bill their insurance company or other third parties, if appropriate, for the care they get for the injury. We will try to have these costs paid for, but subjects may be responsible for some of them.

Injuries sometimes happen in research even when no one is at fault. There are no plans to pay subjects or give them other compensation for an injury, should one occur. However, they are not giving up any of their legal rights by signing this form.

If subjects think they have been injured or have experienced a medical problem as a result of taking part in this research study, they are to tell the person in charge of this study as soon as possible.

**14) Monitoring the data for subject safety**

The principal investigator will oversee the collection, maintenance, and analysis of all data. The UA HSPP will be contacted immediately in the case of unexpected adverse events. This is not a treatment trial.

Additionally, a medical monitor, [name]., has been designated for this study. [name] is required to review all anticipated problems involving risk to volunteers or others, serious adverse events and all volunteer deaths associated with the protocol and provide an unbiased written report of the event to the USAMRMC Office of Research Protections (ORP) Human Research Protection Office (HRPO). At a minimum the medical monitor should comment on the outcomes of the event or problem and in the case of a serious adverse event or death comment on the relationship to participation in the study. The medical monitor should also indicate whether he/she concurs with the details of the report provided by the study investigator. Reports for events determined by either the investigator or medical monitor to be possibly or definitely related to participation and reports of events resulting in death should be promptly forwarded to HRPO.

Subjects may refuse to answer any questions that make them uncomfortable. In addition, subjects may terminate their participation in the study at any time. If significant psychopathology (e.g., threat of harm to self or others) is discovered at any time during or after a subject's visit, we will contact one of the psychiatrists on staff to determine the level of risk and establish a contract for safety. If the subject does not already have an established relationship with a psychiatrist, we will provide the appropriate referrals for psychiatric evaluation.

Assessment of MRI scanning-related safety issues will occur at every scanning session by the study staff. Risks to subjects will be minimized by following standard MRI procedures. Individual scans will be aborted if any safety parameters are breached. If the safety issue involves the patient that cannot be eliminated within the time course of the study, their involvement in the study will be terminated. If the safety issue involves the scanner or the scanning environment, no further scans will

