Interestingly, preliminary data from our own laboratory examining the effects of a 10 minute pulse of blue-wavelength light (469 nm), using the goLITE BLU device proposed for the present study, demonstrates significant increases in brain regions involved in emotional control, alertness, and self-awareness, including the lateral prefrontal cortex, thalamus, and posterior cingulate gyrus during a conflict monitoring task (see figure).

This same cognitive task will be used as part of the proposed study during fMRI scanning. We propose that direct intervention to improve the sleep difficulties in mTBI via blue light therapy may lead to entrainment of the circadian rhythm, improved sleep, and enhancement of daytime alertness. These improvements are predicted to lead to improved emotional regulation, neurocognitive performance, and accelerated improvement in symptoms among patients with mTBI.

The primary aims of the proposed study are to examine the effectiveness of a six-week course of morning blue light therapy (MBLT) on objective and subjective measures of sleep, emotional functioning, mood, psychiatric symptom expression, and neuropsychological assessment using the most current version of the Automated Neuropsychological Assessment Metric (ANAM4) TBI battery. In addition, changes in behavioral functioning produced by MBLT will also be correlated with changes in Blood Oxygen Level Dependent (BOLD) functional magnetic resonance imaging (fMRI) during an executive control task, a virtual reality water-maze task that assesses hippocampal memory function, and a working memory n-back task. These tasks have been used extensively in our

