**FORM: Application for Human Research**

NUMBER	FORM DATE	PAGE
F200	02/2014	9 of 39

laboratory and provide excellent resolution for evaluating functional changes within the target regions of the anterior cingulate gyrus, hippocampus, and prefrontal cortex. Furthermore, the proposed project will directly assess sleep functioning using actigraphy and correlate these changes in sleep with pre-to post-treatment changes in neurocognitive performance and symptom presentation, as well as functional activity changes.

Briefly, individuals who have experienced a mTBI, with or without loss of consciousness, as verified by a medical report, and who complain of sleep disturbance, will undergo an initial psychological assessment, and will be then fitted with an actigraph to wear for the duration of the study in order to measure baseline sleep as well as any changes in sleep patterns. Individuals will then return to complete two comprehensive neurobehavioral assessment and neuroimaging sessions (functional MRI, structural MRI/diffusion tensor imaging; DTI) separated by 6 weeks. During the intervening 6 weeks, participants will be randomly assigned to receive 30 minutes of morning blue light therapy (MBLT) or a sham placebo amber light treatment (SPLT) daily. Sleep quality and quantity will be measured via continuous wrist actigraphy monitors and self-report inventories.

For interested subjects participating in the last phase of recruitment, we will continue collecting wrist actigraphy and self-report data for an additional 6 weeks after completion of the baseline period and light therapy as an optional part of the study. It is hypothesized that MBLT will improve sleep quality and quantity relative to SPLT, and these improvements will be associated with changes in brain function, brain structure, and reduced post-concussion symptom severity at follow-up assessment.

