## FORM: Application for Human Research

NUMBER	FORM DATE	PAGE
F200	02/2014	19 of 39

consent during an initial assessment session and will then be scheduled for a baseline assessment/scanning session.

At baseline, participants will complete a comprehensive neuropsychological test battery, including personality and psychodiagnostic testing, a modified sleep latency test (MSLT), and will undergo two scanning sessions, including 3T fMRI, structural MRI, and DTI scans.

Over the next 7 weeks, participants will wear a wrist actigraph for sleep monitoring and complete daily sleep diaries. During the 6 weeks between the second and third session participants will use a commercially available light therapy device for 30 minutes daily, within 2 hours of awakening, but prior to 10:30 A.M. each day. Subjects will be contacted by phone about once per week for a brief follow up to make sure that everything is progressing well and to answer any questions that arise.

After the treatment period, participants will return for a follow-up assessment/scanning session similar to that conducted at baseline.

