**I. BIOSTATISTICAL ANALYSIS**

Several global outcomes and their interpretations include:

- 1) “If the effects of MBLT versus SPLT are not different and improvement is observed in both groups”—this would suggest that nonspecific effects (practice, maturation, recovery) occurred but were unrelated to the MBLT treatment. Thus there is no specific benefit to the use of MBLT versus placebo. Based on such an outcome, there would be no recommendation for the use of MBLT for treatment of post-concussive symptoms. Secondary analyses correlating cognitive/symptom improvement with changes in brain structure and function may identify new avenues of research and would still contribute valuable knowledge regarding these relationships.
- 2) “If effects of MBLT versus SPLT are not different and no significant improvement is observed in either group”—this finding is less likely, as continued improvement between the two sessions would be expected due to gradual recovery during the first year and due to practice effects associated with repeated assessment. While such a finding would clearly suggest that there is no specific benefit to the use of MBLT versus placebo, it would raise suspicion that the assessments were invalid or insensitive.
- 3) “If MBLT is better than SPLT”—this is the hypothesized effect. This would support the hypothesis that MBLT is beneficial in the treatment of post-concussive symptoms relative to placebo. Regression analysis between the change in symptoms/neurocognitive function and measures of sleep and mood would identify whether this was due to sleep related changes or whether the changes were due to the mood altering effects of MBLT, or both. Similarly, changes in one condition and not the other will also be examined for their relationship to

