**FORM: Application for Human Research**

NUMBER	FORM DATE	PAGE
F200	02/2014	31 of 39

likely preclude an individual from voluntarily gazing directly at a single diode for more than a few moments.

- 2) Participants will be informed about the potential for visual discomfort and possible hazards of long term direct staring at the diodes. This information will be listed prominently in the informed consent document and will be described orally to the participant as well.
- 3) Participants will be given a hands-on demonstration about how to use the device. During the interactive demonstration, the participant will practice the correct method for viewing and will be warned about not staring for prolonged periods at the diodes.
- 4) Participants will be given written instructions with a visual diagram outlining normal safe positioning and use of the device.

5) A warning label will also be printed and taped to the face of each device which states  
“WARNING: DO NOT STARE DIRECTLY AT THE LED SCREEN”

Participants will be instructed on proper use of the device and the importance of not looking directly at the LEDs for extended periods. Of course, individuals differ in their sensitivity to light and it is possible that unanticipated eye fatigue or irritation could occur. Direct staring at the diodes could lead to the presence of temporary afterimages. Participants will be instructed to discontinue use and contact the principal investigator immediately if any unusual sensations or discomforts are noticed.

The MR imaging procedure does not pose a significant risk to subjects meeting the entry criteria for this study. There is no known hazard associated with MR imaging. Nuclear magnetic resonance imaging does not involve ionizing radiation such as that associated with X-ray or radionuclide techniques. All studies will use radiofrequency power deposition and gradient switching which have been approved by the FDA. We do not know if MRI scanning presents a risk to unborn fetuses, so we will ask all females of childbearing potential to complete a urine pregnancy test immediately prior to the scan. This pregnancy test will be performed in the Department of Psychiatry.

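### Eye symptoms from the lamp are accepted as possible, but no fixed question about them and no count by arm against sham is specified

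*Combined protocol and SAP*

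**What the plan says.** All references are to the combined protocol and SAP.

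- **Design.** Section 1 (Background) states that "participants will be randomly assigned to receive 30 minutes of morning blue light therapy (MBLT) or a sham placebo amber light treatment (SPLT) daily". The Biostatistical Analysis section says of a result favouring blue light: "This would support the hypothesis that MBLT is beneficial in the treatment of post-concussive symptoms relative to placebo".
- **Label.** Section 14 (Monitoring the data for subject safety) says: "The UA HSPP will be contacted immediately in the case of unexpected adverse events. This is not a treatment trial".
- **Accepted risk.** Section 8 (Risks to subjects) says that "it is possible that unanticipated eye fatigue or irritation could occur", and adds that staring at the diodes could leave temporary afterimages.
- **Reporting route.** Section 8 continues: "Participants will be instructed to discontinue use and contact the principal investigator immediately if any unusual sensations or discomforts are noticed". For an injury or medical problem, section 13 says of participants that "they are to tell the person in charge of this study as soon as possible".
- **Staff contact.** Section 7 says: "Subjects will be contacted by phone about once per week for a brief follow up to make sure that everything is progressing well". Its part on the six-week light exposure gives the content of the weekly call as adherence, queries and an Epworth Sleepiness Scale score. The rating after each lamp session is for sleepiness only.
- **Oversight.** Section 14 provides a medical monitor, reporting by the investigator to the ethics office, and onward reports to the funder's human research protection office (HRPO).
- **Analysis.** The Biostatistical Analysis section sets out four possible outcomes and how each would be read, then data sharing. It states no summary of harms, overall or by arm.

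**The concern.** The plan names a mild harm of the randomised exposure and then relies on the participant to report it. The lamp is used daily at home for six weeks, so most of the exposure falls between visits. Section 14 has staff assess MRI safety at every scanning session, but states no equivalent routine for the lamp.

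Mild symptoms that nobody asks about at the time are hard to recover later. Volunteered reports are also hard to interpret. Section 1 says many of these patients already have fatigue, dizziness and chronic headaches, so one report cannot show whether the lamp caused the complaint. Putting the same question to both arms, once before the lamp is issued and again during use, gives a fairer comparison.

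The two lamps differ in peak wavelength (469 against 566 nm) and in irradiance (1.23 against 0.58 mW/cm²), so tolerability could differ by arm. At stake is an even-handed statement on tolerability against sham.

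**Working it through.** The plan gives no adverse-event rate and no harms calculation, so there is no figure of its own to reproduce. The check is mainly a comparison of passages.

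**1. Label against design.** Section 14 says the study is not a treatment trial. Sections 1 and 7 describe random allocation to blue light or sham. The stated primary aims concern the effectiveness of a six-week course, and the analysis section speaks of benefit in treatment relative to placebo. The label and the design conflict. Section 14 gives no narrower meaning, regulatory or otherwise, that would reconcile them.

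**2. Where could a lamp-related eye symptom be recorded?**

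| Contact | Stated content | Fixed visual item stated? |
|---|---|---|
| Baseline and post-treatment visits | Rivermead questionnaire; 21-item ANAM symptom checklist | Items not listed in the text |
| Daily, before and after the lamp | Stanford Sleepiness Scale; sleep and wake times | No |
| Weekly call | General check, adherence, queries, Epworth scale | No |
| Any time | Participant stops and contacts the investigator | Participant-initiated |

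General symptoms are covered evenly in both arms at the two visits. Between visits, no fixed question on visual symptoms is stated.

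**3. Is there a comparison by arm?** Events are handled singly under section 14. The medical monitor must comment on relationship to participation for serious events and deaths; a brief afterimage would be neither. No count by arm is planned.

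**4. What could a table by arm show?** Inputs from section 5: 40 run and 30 complete. Section 7 assigns half to each lamp, so 40/2 = 20 or 30/2 = 15 per arm. With zero events among n people who were all asked, the exact one-sided 95% upper bound on the true rate is 1 − 0.05^(1/n):

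- n = 20: 1 − 0.05^(1/20) = 0.139, or 13.9%
- n = 15: 1 − 0.05^(1/15) = 0.181, or 18.1%

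Even complete questioning with no events would leave a true rate of 14% to 18% in an arm compatible with the data. The table describes; it does not test.

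**5. Workload.** Six weekly calls for 40 people: 40 × 6 = 240. Baseline and post-treatment visits: 40 × 2 = 80. Total 240 + 80 = 320 existing contacts at most. At an assumed 2 to 3 minutes each, including logging: 320 × 2 = 640 to 320 × 3 = 960 minutes, or 10.7 to 16.0 hours over the whole study.

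**The case against.** The case on the other side is substantial, and much of it stands.

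- **Both arms already have uniform symptom ratings.** The Rivermead questionnaire and the ANAM checklist are given before and after treatment, so general complaints can be compared by randomised arm. This stands, and it confines the gap to visual symptoms, chiefly between visits.
- **The weekly call is close to an open question.** Staff ring everyone in both arms. This stands in part: a general check may bring out a complaint, but no fixed item and no log is stated.
- **Some attachments are unseen.** Those listed in Section 4 include the scan-day questionnaires, the sleep diary, a phone script, the watch and light guide and the lamp instructions. One of them may already ask about eyes. This stands as a limit on the point.
- **The lamp is low risk.** Section 8 puts the blue device at 8.9% of the long-term exposure limit, and section 7 reports that it met the criteria for an exempt product. This stands. The documents give no reason to expect a serious hazard to be missed.
- **The label changes no procedure.** This stands too. Correcting it is editorial.

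Two stronger readings are tempting. A reader might infer from the label that safety oversight is absent or was relaxed. The same section sets up a medical monitor and reporting to the ethics office and HRPO, and nothing shows that any procedure was weakened. A reader might also infer that the analysis looks only for improvement. Its fourth outcome is sham doing better than blue light, with the direction of effects to be examined. That is not an adverse-event comparison, but it does allow for the active arm doing worse.

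**Conclusion.** The point holds in a limited form and is **minor**. For a harm the plan accepts as possible, the specified capture is participant-initiated, the weekly calls have no stated visual item, and no comparison of harms with sham is planned. The gap is uniform ascertainment of lamp-related visual symptoms, mainly between visits, and counting them by arm. It is not a gap in safety oversight as a whole.

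The number of symptoms that would go unrecorded cannot be estimated, because the documents give neither a symptom rate nor the share of people who would volunteer one. The only firm figure is the ceiling on what the data could show: upper bounds of 13.9% with 20 per arm and 18.1% with 15, assuming zero events and everyone asked.

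The conclusion assumes that no unseen attachment already asks both arms about eye symptoms. If one does, only the counts by arm and the wording of section 14 remain to be put right.

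**What to change.** 1. At the baseline visit before the lamp is handed over, at each existing weekly call and at the post-treatment visit, ask every main-arm participant, in identical words in both arms, one fixed question on visual symptoms and one on whether there are any new problems.
2. Log the answers with dates. Report counts descriptively by arm for everyone given a lamp, including those who stop early.
3. Leave the section 14 reporting routes as they are. Events that meet those rules go to the medical monitor and the ethics office as already planned.
4. Replace the label in section 14 with: *The main arm is a randomised, sham-controlled comparison of light treatments.*

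**Cost.** A few minutes at each existing contact, about 11 to 16 staff hours in all on the assumption shown above, plus one short form and one table. No visit is added. The change needs IRB approval (section 6), and HRPO approval before use if it counts as a major amendment (section 7). The downside is that more minor events will be recorded in both arms.
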